RESEARCH PROPOSAL

Title: Immediate Effect Of Standing Trunk Extension Postures On Spinal Height And Clinical Outcome Measures In Low Back Pain: A Randomized Clinical Trial

Investigators:

[name], PT, ScD - PI

[name], PT, DPT

[name], PT, PhD

Clinical Musculoskeletal Research Laboratory, Center for Rehabilitation Research, School of Health Professions, TTUHSC, Lubbock, TX, USA

TABLE OF CONTENTS

ABSTRACT.....4

LIST OF FIGURES.....5

LIST OF ABBREVIATIONS.....6

BACKGROUND.....7

PURPOSE, AIMS, VALUES.....12

RESEARCH QUESTIONS.....13

HYPOTHESES.....13

COMPARISON VARIABLES.....14

 Independent Variables.....14

 Dependent Variables.....15

 Relationship Variables.....15

METHODS.....16

 Research Design.....16

 Pre-Study Approvals.....16

 Subjects.....16

 Testing Sequence.....17

DATA ANALYSIS.....22

RESEARCH PROJECT TIMELINE.....25

REFERENCES.....26

APPENDICES.....41

ABSTRACT

Background: Standing trunk extension postures have been used for many years as a mechanical approach to low back pain (LBP), sometimes directed by therapeutic intervention, sometimes subconsciously performed by patients to relieve LBP. However, no study to date has investigated the effect of standing trunk extension postures on spinal height and clinical outcome measures.

Objective: The purpose of this study will be to evaluate in subjects with LBP following a period of trunk loading, how spinal height and/or pain, symptoms' centralization, and function outcome measures respond to: (1) standing repetitive trunk extension posture; and (2) standing sustained trunk extension posture. Lumbar range of motion (ROM) achieved during these two trunk extension postures will be compared to spinal height and outcome measures.

Methods: A pre-test, post-test comparison group design (randomized clinical trial) will be used to determine how spinal height changes in response to sustained and repetitive standing trunk extension after a period of spinal loading. The study will use a 2 (between subjects – type of trunk extension: sustained vs. repetitive) x 3 (within subjects - time: before vs. after vs. 2 weeks after intervention) mixed design to evaluate the effects of sustained and repetitive trunk extension in standing on spinal height, pain, symptoms' centralization and function.

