Statistical Analysis: A 2(Strategy) X 3(Time) mixed ANOVA will be used to statistically identify significant interactions and main effects for spinal height, pain and function outcome measures. Post-hoc pairwise comparisons will be used to locate significant differences between the different conditions (Time). Significance will be set at $\alpha = 0.05$. Pearson product-moment correlations will be used to measure correlations between lumbar ROM in relation to spinal height and outcome measures. The Kruskal-Wallis 1-factor ANOVA for difference scores will be used to determine changes of intensity and location of symptoms following sustained versus repetitive standing trunk extension. Spearman Rank correlation will be used to evaluate the relationship between spinal height changes and changes of pain and location of symptoms for each group.

Word Count: 326

Key Words: Standing postures; trunk extension; spinal height change; stadiometer

Lay Summary

Standing back extension postures have been used for many years to treat people with low back pain.

No study to date has investigated the effect of standing back extension postures on trunk height, pain and function.

The **purpose** of this study will be to evaluate in subjects with low back pain how trunk height, pain and function respond to standing repetitive versus sustained trunk extension postures.

Methods: A randomized clinical trial will be used to determine how trunk height, low back pain and function change in response to sustained and repetitive standing trunk extension after a period of spinal loading.

Statistical Analysis will be used to measure the outcomes.

LIST OF FIGURES

Figure 1: Flowchart depicting testing sequence.....31

Figure 2: Starting position for standing trunk extension (repetitive and sustained).....34

Figure 3: Sustained trunk extension position and end position of repetitive trunk extension.....35

Figure 4: Position of subject for spinal height measure in stadiometer unit.....36

Figure 5: Position of subject during spinal loading time in sitting.....37

Figure 6: Home exercise program for repetitive trunk extension group.....38

Figure 7: Home exercise program for sustained trunk extension group.....39

Figure 8: Home instructions for each subject.....40

LIST OF ABBREVIATIONS

Analysis of Variance.....	ANOVA
Fear Avoidance Belief Questionnaire.....	FABQ
Intervertebral Disc.....	IVD
Institutional Review Board.....	IRB
Low Back Pain.....	LBP

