One investigator will be involved with data collection. The investigator, [name], PT, DPT will carry out inclinometer measurements of lumbar and sacral posture, supervised positioning in the stadiometer and stadiometric measurements. The investigator will be blinded to the intervention (each subject will receive a hidden random number and will perform independently the intervention in a treatment room) and the stadiometric measurements during the experiment. He will also be responsible for assigning subjects to their initial groups, supervising the subjects' positioning in the different standing postures and confirming that a stadiometer reading is recorded on an Excel spreadsheet.

Subjects Compensation

Subjects will receive a one-month free membership to Hill Country Memorial Wellness Center in Fredericksburg, Texas if they consent to participate in the study.

Subjects Charges

There will be no charge for the two physical therapy sessions, including

examination and intervention. Following the two intervention sessions, subjects referred by primary care providers (physicians, chiropractors, nurse practitioners, physician assistants) to physical therapy for LBP will have the choice to receive standard care and be charged for physical therapy intervention.

Confidentiality and data protection

Electronic Transmission of Personally Identifiable Information (PII) and Protected Health Information (PHI) will be followed and computer device has been encrypted (password protected). Excel spreadsheet will be used to store the data. No Personally Identifiable Information will be retained in the Excel spreadsheet where the data will be stored.

Data Analysis

Descriptive and inferential statistics will be used utilizing SPSS 23.0 for Windows (SPSS, Chicago, IL).

1. **Descriptive analyses:** Descriptive statistics including mean, median, mode, standard deviation, minimum and maximum values, frequency counts will be collected for age, height, weight, body mass index, pain, centralization, function (Oswestry Low Back Pain Disability Questionnaire), Fear Avoidance Beliefs Questionnaire, spinal height, and spinal height changes after repetitive and sustained standing trunk extension after a period of spinal loading.
2. **Inferential analyses:** Levene's test and Shapiro-Wilk test of normality will be used to test for variance and distribution of measurements of spinal height,

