Measurement 4

Trunk Ext Measure 2 Using Inclinometers

Measurement 4

Trunk Ext Measure 2 Using Inclinometers

Figure 2: Starting position for trunk extensions.

Figure 3: Sustained trunk extension position and end position of repetitive trunk extensions.

[figure not shown]
Figure 4: Position of subject for spinal height measure in stadiometer unit.

Figure 5: Position of subject during spinal loading time in sitting.

Figure 6: Home instructions for Repetitive Trunk Extension

STANDING REPETITIVE EXTENSIONS

-Start by standing with your feet shoulder width apart and place your hands on your hips. Lean back to arch your back then return to starting position. (Lean back as far as you can tolerate with each repetition)

[figure not shown]
Sets: 1

Repetitions: 10 (Performed in 45 seconds, rest 15 seconds)

-Perform sets in succession

Frequency: 5 times per day

Figure 7: Home instructions for Sustained Trunk Extension

STANDING SUSTAINED EXTENSIONS

-Start by standing with your feet shoulder width apart and place your hands on your hips. Lean back to arch your back, HOLD for time listed below, then return to starting position. (Lean back as far as you can tolerate with each repetition)

Sets: 1

Repetitions: 1 (hold extension 45 seconds, rest 15 seconds)

-Perform sets in succession

Frequency: Five times per day

Figure 8: Home instructions

Continue to use your medications, including medications aimed at decreasing your pain, as prescribed by your primary healthcare provider/physician. Please avoid changing them during the follow-up two-week period.

We will ask you to complete a sheet recording home exercise compliance when you come to the second treatment session in about two weeks.

Thank you.

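### The sole data collector is declared blind to arm, yet assigns groups and supervises the standing postures, so assessor blinding is not assured as written

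*Combined protocol and SAP*

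**What the plan says.** The Investigator Blinding section opens with "One investigator will be involved with data collection". That person "will carry out inclinometer measurements of lumbar and sacral posture, supervised positioning in the stadiometer and stadiometric measurements". The section then makes two masking claims about him, one for the arm and one for the stadiometer values. The first reads "The investigator will be blinded to the intervention (each subject will receive a hidden random number and will perform independently the intervention", and the place given is a treatment room. The sentence after it adds: "He will also be responsible for assigning subjects to their initial groups, supervising the subjects' positioning in the different standing postures".

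Testing Sequence, Session 1, describes assignment differently. A web-based randomization plan generator allocates each subject, and subjects write down their own intervention number so that the investigator stays blind. The same section covers the stadiometer display and has the device record the data automatically.

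**The concern.** The arm-blinding claim depends on the data collector having no part in assignment and not watching the intervention. The duties listed immediately afterwards appear to give him both roles. If the text is followed as it stands, a report could not rest on it to say that the assessor was blind to arm. This matters because RH 2 predicts opposite between-arm differences: more height gain with sustained extension, and more improvement in pain, centralization and function with repetitive extension. Readers of such a comparison rely on a statement of assessor blinding.

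**Working it through.** The plan gives no figure to reproduce. The check sets the statements side by side.

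1. **Mechanism against duties.** Exercising independently conflicts with being supervised in posture, unless the supervision happens at some other moment. A concealed number conflicts with being assigned to a group by the measurer, unless he passes on a code whose meaning he does not know.

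2. **What the standing postures are.** The Objective in the Abstract names the arms as "standing repetitive trunk extension posture; and (2) standing sustained trunk extension posture", and RH 2 uses the same term. The other stages of the test are not standing: unloading is supine and loading is seated. The inclinometer and stadiometer duties are listed in an earlier sentence, and the supervising duty is then introduced as an additional one. The arms are therefore the natural referent, though not the only possible one.

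3. **Whether seeing the intervention reveals the arm.** From Session 1:
   - Repetitive arm: 10 extensions per 45 seconds, five times, so 10 × 5 = 50 extensions.
   - Sustained arm: 5 holds of 45 seconds.
   - Time in either arm, counting a rest after each set: 5 × (45 + 15) = 300 seconds, or 5 minutes.

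   Duration does not disclose the arm, but watching the movement does.

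4. **Readings under which blinding survives.**
   - The supervised postures could be those held for the inclinometer readings. The section itself uses the word *posture* for that measurement.
   - They could be the positions common to both arms. The List of Figures describes Figure 2 as "Starting position for standing trunk extension (repetitive and sustained", and the other caption is "Figure 3: Sustained trunk extension position and end position of repetitive trunk extensions". Checking only these need not reveal the arm.
   - *Assigning* could mean handing out coded numbers.

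   Blinding needs one of the first two readings together with the third. The text states none of them.

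5. **What would be exposed if he knew the arm.**
   - *Height:* subjects reposition themselves, the display is covered and recording is automatic. The remaining route is his supervision of positioning for Measurement 4, which follows the intervention. Subjects enter only with a repositioning SD of 1.3 mm or less over five consecutive measurements. That limits random scatter at familiarization. It does not by itself exclude a systematic shift later, and no such shift is shown.
   - *Trunk extension:* Figure 1 places "Trunk Ext Measure 2 Using Inclinometers" after Measurement 4, and no masking is described for it. Under Data Analysis it serves the correlations of hypothesis 3, not a comparison of arms.
   - *Pain and the modified Oswestry:* both are self-reported, so they do not pass through his judgement.

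**The case against.** The strongest reply is that this is loose drafting with no consequence. The protocol says three times that the arm is hidden: a generator assigns, the number is concealed, and the subject records it expressly to keep the investigator blind. The supervised postures may well be the measurement postures. The home-exercise compliance form is the same for both arms, and the main readings are masked or self-reported.

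Much of this stands. It rules out saying that blinding fails, and it limits the consequence to two steps. It does not remove the conflict. The statement of blinding and the duties that undercut it are consecutive sentences about the same person, and nothing elsewhere says which governs. This is more than a missing detail.

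A reader might go further and infer that allocation was not concealed and that selection into arms was possible, because an investigator judges directional preference for entry. The documents do not support that inference. It would require the person judging entry to be the measurer, which cannot be confirmed because names are removed from the public copy. It would also require him to see the list, which is not stated. As described, screening comes before assignment. That order does not exclude foreknowledge of a list made in advance, but nothing says he had any. List custody is a request for clarification and not part of the contradiction.

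**Conclusion.** The point holds in limited form: as written, the protocol does not assure that the sole assessor is blind to arm. This rests on reading the standing postures as the interventions, which is the protocol's own usage but not the only reading, and on *assigning* carrying its ordinary meaning. A reader might conclude that the blinding was broken or the results biased. Neither follows, because readings exist under which blinding holds. No bias is shown, and its size cannot be derived from the documents. The possible exposure is supervised positioning for Measurement 4 and the post-intervention inclinometer reading. The separate claim that stadiometer values are masked is supported by the covered display and automatic recording, and is not in question.

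**What to change.** Reconcile the Investigator Blinding section with the randomization text in Session 1 by one of two routes.

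(a) **Keep the claim.** State that the measurer stays out of the treatment room during the intervention. Limit his supervision to the measurement positions, or to the start and end positions common to both arms. Reword *assigning* as handing out the next concealed number. Keep that number and the arm-specific home sheet (Figures 6 and 7) out of his sight. The cost is less checking of posture during the intervention.

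(b) **Drop the claim.** Delete the statement that he is blind to the intervention, report the assessor as unblinded to arm, and keep only the statement that stadiometer values are masked. This is a wording change and needs no staff.

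As a secondary clarification under either route, state who generates and holds the randomization list. The proposal lists three investigators, so this need not be the measurer.

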function testing outcomes immediately and two weeks following the interventions in patients with LBP.

2. **RH 2:** It is expected that following a period of trunk loading, sustained standing trunk extension posture in standing will result in greater spinal height gain as compared to repetitive standing trunk extension postures, while repetitive standing trunk extension postures will result in greater improvements in pain, centralization and function testing outcomes as compared to sustained standing trunk extension postures immediately and two weeks following the interventions.
3. **RH 3:** It is expected that following a period of trunk loading, there will be a positive correlation between the degree of trunk extension during standing trunk extension posture and spinal height, centralization, pain and function testing outcomes changes immediately and two weeks following the interventions in patients with LBP.

Comparison Variables

Independent Variable(s)-The student plans to use the following Independent variable(s) (IV)

1. IV1: Trunk extension
 - a. IV1: sustained
 - b. IV2: repetitive
2. IV2: Time

- a. IV1: before
- b. IV2: after (immediately)
- c. IV3: after 2 weeks

Dependent Variable(s)-The Student plans to measure the following dependent variable(s) (DV)

1. DV1: Spinal height using stadiometer (ratio scale).
2. DV2: Pain rating using numerical pain rating scale (NPRS) (ordinal scale).
3. DV3: Centralization (ordinal) using body diagram.
4. DV4: Modified Oswestry Pain Disability Questionnaire (ordinal scale)

Relationship Variable(s)- (RV) (if applicable)

1. RV1: Degree of spinal extension (ratio)
2. RV2: Spinal height using stadiometer (ratio scale).
3. RV3: Pain rating using numerical pain rating scale (NPRS) (ordinal scale).
4. RV4: centralization (ordinal).
5. RV5: Modified Oswestry Pain Disability Questionnaire (ordinal scale)

METHODS

Research Design(s)

A pre-test, post-test comparison group design (randomized clinical trial) will be used to determine how spinal height changes in response to sustained and repetitive standing trunk extension after a period of spinal loading. The study will use a 2 (between subjects – type of trunk extension: sustained vs. repetitive) x 3 (within subjects - time: before vs. after vs. 2 weeks after) mixed design to evaluate the effects of sustained and repetitive trunk extension in standing on spinal height, pain, centralization and function outcome measures.

Pre-study Approvals

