defined as either (1) a specific direction of trunk movement or posture noted during the physical examination or (2) a specific easing factor reported by the patient during the subjective history that alleviates or decreases the patient's pain, with or without the pain having changed location and/or increased the patient's lumbar range of motion (Werneke 2011). A questionnaire including pertinent medical history will be completed (Appendix C). Subjects will complete (1) a Numerical Pain Rating Scale (NPRS) to rate their current, minimum, maximum and average LBP over the last two days (Ferreira-Valente MA 2011) as well as paresthesia signs/symptoms intensity (Appendix D); (2) Body Diagram for indicating location of symptoms (Appendix E); (3) Modified Oswestry low back pain questionnaire (Fritz 2001) (Appendix F); (4) Fear Avoidance Belief Questionnaire (Cleland et al 2008) (Appendix G). A researcher will record subject's height and weight. A Flow chart illustrates study sequence in details (Figure 1).

If the subject meets criteria for inclusion in the study, the subject will complete a familiarization procedure to determine the consistency to reposition themselves in the stadiometer. Subjects able to reposition themselves in the stadiometer with a SD of 1.3mm or less for five consecutive measurements (Stothart et al 2000; Gerke et al 2011; Owens et al 2009) will be included in the study. The digital display will be covered to blind the researcher performing the measurements. The data will be automatically recorded by the stadiometer and manually downloaded to a laptop computer.

At the beginning of data collection, a randomization plan generator

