The subject will reposition on the stadiometer and spinal height will be measured (Measurement 4). Trunk extension will be measured to determine the strength of correlations between the degree of trunk extension during standing trunk extension posture and spinal height, pain and centralization testing outcomes changes (MacDermid et al 2015). The subject will score their low back and lower extremity symptoms using NPRS (Ferreira-Valente MA 2011), and *map their pain* on a body pain diagram (Appendix E) prior to intervention, immediately after and 2-week following the intervention to determine pain rating and centralization of symptoms (Simmerman et al 2011). The principal investigator will apply a numeric overlay template to the patient's body diagrams to document the most distal pain location scores between 1 and 6 (Appendix I). Higher score will indicate a more distal symptoms' location.

Home instructions

Subjects will be instructed to continue to use their medications, including medications aimed at decreasing their pain, as prescribed by their primary healthcare provider and not to change them during the follow-up two-week period. A sheet including home exercise instructions will be provided to each patient. Instructions will include repetitive or sustained trunk extension based on random group assignment, performed approximately 5 times per day. Each subject will complete a sheet recording home exercise compliance upon arrival in

session 2 (Appendix I).

Session 2

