Subjects will complete: (1) a NPRS to rate their current, minimum, maximum and average LBP over the last two days as well as paresthesia signs/symptoms intensity (Appendix D); (2) Body Diagram for indicating location of symptoms (Appendix E) (3) Modified Oswestry low back pain questionnaire (Fritz 2001) (Appendix F); (4) Fear Avoidance Belief Questionnaire (Cleland et al 2008) (Appendix G). Each subject will then complete a familiarization procedure to determine the consistency to reposition themselves in the stadiometer as described in session 1. The subject will undergo a 10-minute period of trunk unloading in a supine posture to ensure spinal height is normalized as described in session 1. The subject will reposition on the stadiometer and spinal height will be measured after a relaxed exhalation (Measurement 1) (Figure 4). The subject then will undergo a five-minute period of loaded upright sitting with a 4.5kg bag secured on each shoulder and spinal height will be measured (Measurement 2) (Figure 5). The subject will then undergo an additional five minutes sitting without load and spinal height will be measured (Measurement 3). Inclinometers will be used to take an initial measure of each subject trunk extension prior to intervention. The subject will then undergo the same intervention as in session 1 for 5 minutes as previously described (standing repetitive trunk extension or standing sustained trunk extension). The subject will reposition on the stadiometer and spinal height will be measured (Measurement 4). Trunk extension will be measured to determine the strength of correlations between the

degree of trunk extension during standing trunk extension posture and spinal height, pain and centralization testing outcomes changes (MacDermid et al 2015). The subjects will then score their low back and lower extremity symptoms using NPRS (Ferreira-Valente MA 2011), and *map their pain* on a body pain diagram (Appendix H).

Investigator Blinding

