changes in spinal height, degrees of spinal extension, pain, and function outcomes.

For *experimental hypothesis 1*, a paired-t-test (or Wilcoxon sign-rank test if the data do not meet assumptions for parametric inferential statistics) will be used to assess differences in spinal height, centralization and pain outcomes improvements following sustained and repetitive trunk extension postures.

For *experimental hypothesis 2*, 2 (between subjects - type of trunk extension: sustained vs. repetitive) x 3 (within subjects - time: before, immediately after and 2-week after) mixed ANOVA's will examine differences in (1) spinal height; (2) pain; and (3) function outcomes, as a result of sustained and repetitive standing trunk extension after a period of spinal loading. Post hoc paired t-tests will explore further for significant differences in spinal height, pain and function outcomes between the six conditions.

Experimental hypothesis 3 will be tested with Pearson product-moment correlations to determine the strength of correlations between the degree of trunk extension during standing trunk extension posture and spinal height, pain and function, outcomes changes in patients with LBP.

Spearman's Rank Order correlation will be used to determine the strength of the correlation between centralization and the degree of trunk extension posture in standing.

Alpha level will be set at 0.05 for significance for all tests and Bonferroni corrections performed as needed.

REFERENCES

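### Function is planned for a three-time-point ANOVA, but the session descriptions collect the Modified Oswestry at only two time points

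*Combined protocol and SAP*

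**What the plan says.** **Analysis.** The Abstract's Statistical Analysis paragraph plans a 2 (Strategy) x 3 (Time) mixed ANOVA to find "significant interactions and main effects for spinal height, pain and function outcome measures". Under experimental hypothesis 2, the Data Analysis section names the three times as before, immediately after and two weeks after, and says that the ANOVAs "will examine differences in (1) spinal height; (2) pain; and (3) function outcomes". It adds post hoc paired t-tests, function included, across six conditions. The Abstract's Methods paragraph describes a "mixed design to evaluate the effects of sustained and repetitive trunk extension in standing on spinal height, pain, symptoms' centralization and function", and Research Design describes a "mixed design to evaluate the effects of sustained and repetitive trunk extension in standing on spinal height, pain, centralization and function outcome measures". RQ 1-3 and RH 1-3 all refer to function both immediately and at two weeks.

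**Measure.** Function has one instrument: "DV4: Modified Oswestry Pain Disability Questionnaire (ordinal scale"). The descriptive analyses paragraph also equates function with the Oswestry.

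**Schedule.** The Session 1 intake lists the body diagram and then the Oswestry ("Appendix E); (3) Modified Oswestry low back pain questionnaire"). The Session 2 intake does the same ("Appendix E) (3) Modified Oswestry low back pain questionnaire"). The pain rating scale and body diagram have an explicit three-time schedule: "prior to intervention, immediately after and 2-week following the intervention to determine pain rating and centralization of symptoms". No such sentence exists for the Oswestry, and neither session lists it after the intervention.

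**The concern.** A repeated-measures ANOVA needs a value at every level of the within-subject factor. If function is never measured immediately after the intervention, the planned function model cannot be run and part of every research question and hypothesis has no data.

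The analyst would then choose a replacement with the data in hand. The plan would not say which contrast tests function, how many function comparisons count toward a Bonferroni correction that is applied only as needed, or which change score enters the hypothesis 3 correlation. The function question that the data can answer, change from intake to two weeks by arm, is nowhere stated as the planned analysis.

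**Working it through.** The plan gives no figure to reproduce, so the check compares schedule with analysis.

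**Step 1. Time points by outcome, from the Testing Sequence**

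| Outcome | Before | Immediately after | Two weeks |
|---|---|---|---|
| Spinal height | yes | yes (Measurement 4) | yes |
| Pain rating | yes | yes | yes |
| Body diagram | yes | yes | yes |
| Modified Oswestry | yes (Session 1 intake) | **not listed** | yes (Session 2 intake) |

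The gap is specific to function. The Session 1 and Session 2 sentences on correlations with trunk extension likewise name spinal height, pain and centralization, but not function.

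**Step 2. Cells.** Planned: 2 arms x 3 times = 6. Filled for function: 2 arms x 2 times = 4. Empty: 6 - 4 = 2, the immediate cell in each arm.

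**Step 3. Complete cases.** Subjects / Specimens plans 40 participants completing both days. With all 40 providing both intake scores, the three-level function model has 0 of 40 complete cases and a two-level model has 40 of 40.

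**Step 4. Arm-by-time test.** With G = 2 arms, T times and N = 40, the degrees of freedom are (G - 1)(T - 1) and (N - G)(T - 1).
- T = 3: 1 x 2 = 2 and 38 x 2 = 76, so F(2,76).
- T = 2: 1 x 1 = 1 and 38 x 1 = 38, so F(1,38).

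With two times, the interaction F is the square of the two-sample t statistic on change scores. The 2 x 2 interaction is therefore exactly the between-arm comparison of change.

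**Step 5. Post hoc paired tests.** The plan does not list the pairs. Each participant is in one arm, so I read a paired test as within-arm.
- Three times: 3 pairs x 2 arms = 6 contrasts.
- Two times: 1 pair x 2 arms = 2 contrasts. The other 4 cannot be estimated.
- If Bonferroni were applied across these function contrasts, the threshold would be 0.05/6 = 0.0083 or 0.05/2 = 0.025, depending on which set is counted.

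**Step 6. Hypothesis 1.** RH 1 predicts better function, but the hypothesis 1 test sentence names only spinal height, centralization and pain.

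**Step 7. Time from intake to the immediate point.** The timed steps in Session 1 are 10 minutes supine, 5 of loaded sitting, 5 of unloaded sitting and 5 of intervention: 10 + 5 + 5 + 5 = 25 minutes, excluding familiarization and measurement time.

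**The case against.** **The flow chart may show an immediate Oswestry.** Session 1 refers to Figure 1 for the detailed sequence, and most of it is not readable here. The legible fragments mention no Oswestry, but they also omit the pain rating and body diagram, which the text does schedule, so their silence proves nothing. This limit stands. An administration shown only in the figure would still contradict the text, and one of them would have to change.

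**The design sentences are loose.** The Abstract's Methods paragraph and Research Design also list centralization, which is not in the ANOVA. Being named there does not by itself put an outcome in a three-level model. That is fair. The Abstract's Statistical Analysis paragraph and the hypothesis 2 text do put function there explicitly, and they carry the point.

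**The problem exposes itself.** An empty column cannot produce a false-positive result, and an analyst would simply fit two times. True, and it limits the severity. The replacement would still be unplanned. Because no participant has an immediate score, neither imputation nor a likelihood-based mixed model can recover that level from observed function data.

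**Within-arm function change is already tested.** The post hoc tests for hypothesis 2 cover it, so the hypothesis 1 omission is minor. Accepted; it is a labelling gap to close in the same edit.

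**Measuring function immediately would suit the title better.** The trial is titled around immediate effects, and the form asks about the respondent's condition today. Adding an administration is a legitimate alternative. I do not prefer it because items such as sleeping, traveling and employment are unlikely to register change over about 25 minutes in a clinic. That is a judgement, not a figure in the documents, and items such as sitting and standing could be argued the other way.

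**Conclusion.** The concern holds. On the sessions as described, function has 2 of the 3 planned time levels and 4 of the 6 cells. The three-level function ANOVA cannot be run, and the immediate-function parts of RQ 1-3 and RH 1-3 cannot be answered. The estimable arm-by-time test is F(1,38) rather than F(2,76), and 2 of 6 within-arm paired contrasts remain.

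This rests on the session text being the full schedule, on 40 completers with both intake scores, and on reading the paired tests as within-arm. The before versus two-week comparison of function remains valid, and this gap leaves the spinal height and pain models unaffected. It should be fixed before analysis, but it does not undermine the trial as a whole.

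**What to change.** State that function is analysed at two time points, the Session 1 intake and the Session 2 intake:

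- **Abstract, Research Design and Data Analysis:** give function a 2 x 2 mixed ANOVA, with the interaction as the between-arm comparison of change. An ANCOVA of the Session 2 score adjusted for the Session 1 score is an optional, usually more precise, alternative (error df 40 - 3 = 37). If it is used, name it in advance.
- **Independent variables:** note under Time that function has no immediate level.
- **Within-arm tests:** limit function to before versus two weeks, one test per arm. Do each once, and use it both for hypothesis 1 (adding function to that sentence) and as the post hoc test for hypothesis 2.
- **Hypothesis 3:** limit the function correlation to the two-week change.
- **RQ 1-3 and RH 1-3:** remove the immediate claim for function.
- **Figure 1:** confirm that it shows the same two administrations.

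The cost is wording changes and a check of the figure, with no new data, visits, staff or participants. The alternative is an Oswestry after Measurement 4 in Session 1. It would keep the 2 x 3 model but change the Session 1 schedule, and the plan should then justify the instrument over so short an interval.
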